7.7.3 Subgroup Assessment of Shifts from Baseline in Clinical Laboratory

Shifts from baseline Grade 0 – 2 to post baseline Grade 3 – 4 for the maximum grade in clinical laboratory variables will be assessed for the subgroups defined below:

- Gender (Male, Female)
- Age (< 75 years, ≥ 75 years)
- Race (White, Non-White)
- Region (US, Non-US)

Study M14-358:

1. overall of venetoclax + azacitidine (N = 127);
2. venetoclax 400 mg QD + azacitidine (N = 84);
3. overall of venetoclax + decitabine (N = 73).

Study M14-387:

1. All subjects venetoclax 600 mg QD + LDAC or venetoclax 800 mg QD + LDAC (N = 92)
2. venetoclax 600 mg QD + LDAC (N = 82)
3. venetoclax 600 mg QD + LDAC and without MPN (N = 78).

7.8 Vital Signs Parameter

The vital sign variables that will be assessed are systolic blood pressure, diastolic blood pressure, pulse and temperature. All vital sign summaries will be summarized for analysis sets 2 – 3 specified in [Table 3](#). The vital signs variables summary for Study M14-212 is in study CSR.

7.8.1 Assessment of Potentially Clinically Significant Vital Signs Parameters

For selected vital signs parameters, a listing of all observations collected will be generated for subjects that had at least one post-baseline observation meeting pre-defined criteria for potentially clinically significant values. The number and percentage of subjects in each treatment group who have at least one post-baseline observation meeting the pre-defined criteria for potentially clinically significant values will be provided for each variable.

Pre-defined criteria for potentially clinically significant vital signs parameters are given in [Table 6](#) below:

Table 6. Criteria for Potentially Clinically Significant Vital Signs Parameters

Vital Signs Variables	Criterion	Definition of Potentially Clinically Significant
Systolic blood pressure	High	Value \geq 160 mmHg
Diastolic blood pressure	High	Value \geq 100 mmHg
Heart Rate	Low	Value \leq 50 bpm
	High	Value \geq 120 bpm
Temperature	Low	Value \leq 36°C
	High	Value \geq 38.5°C

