3.3 Benefits and Risks

Based on the venetoclax studies, the regimen is designed to escalate the dose of venetoclax rapidly and safely with a standard dose and schedule of LDC to optimize the opportunity for achieving a response and enable close subject monitoring. The dosing regimen will also enable interruptions and slower intra-subject dose escalation to target assigned dose if rapid tumor lysis is observed. Based on the ex vivo testing of primary subject AML samples that has shown significant variability among subjects, initial signs of leukemia response may occur at different doses of venetoclax when combined with LDC for different subjects.

Venetoclax was administered to 32 subjects with AML as monotherapy in Study M14-212. Safety data from 28 (87.5%) subjects who experienced adverse events of grade 3 and above, showed the most common events being febrile neutropenia (31.3%), malignant

neoplasm progression, (25.0%), hypokalemia, and pneumonia (21.9% each). Serious adverse events were reported for 27 (84.4%) subjects, including febrile neutropenia (9 subjects), malignant neoplasm progression (8 subjects), pneumonia (5 subjects), abdominal pain, sepsis, urinary tract infection, failure to thrive, renal failure acute, and hypotension (2 subjects each). All other events occurred in 1 subject each.

Study M14-212 has completed with efficacy data available for 32 subjects, the majority of them (30, 94%) with R/R AML. The ORR was 19% (6 of 32 subjects), with CR in 2 (6%) and CRi in 4 (13%) subjects. Anti-leukemic activity was observed in an additional 6 (19%) subjects.

For additional safety and efficacy data please refer to the current Investigator Brochure.²⁵

Considering the coronavirus (COVID-19) pandemic, the benefit and risk to subjects participating in this study has been re-evaluated. Subjects receiving venetoclax may be at an increased risk for COVID-19 infection or experience serious illness if infected. Management of these adverse events will be made on a case-by-case basis with consideration of benefit/risk. However, based on the population and disease being studied and the anticipation that COVID-19 related risks are not expected to differ substantially between study subjects and the broader population of subjects receiving treatment for AML, no change to the benefit/risk balance for subjects in this study is expected.

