8.1.4.4 Longitudinal Analyses of Laboratory and Vital Signs Data

Changes from baseline will be analyzed for each scheduled post-baseline visit and for the final visit for blood chemistry and hematology parameters, as well as urinalysis and vital sign parameters. If more than one measurement exists for a subject on a particular day, then an arithmetic average will be calculated. This average will be considered to be that subject's measurement for that day. Post-baseline measurements more than 30 days after the last dose of study drug will not be included. Subjects that do not have a baseline measurement or do not have any post-baseline measurements will not be included.

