Appendix H. Tumor Lysis Syndrome Classification

Metabolic Abnormality	Criteria for Classification of Laboratory Tumor Lysis Syndrome*	Criteria for Classification of Clinical Tumor Lysis Syndrome**
Hyperuricemia	Uric acid > 8 mg/dl (475.8 µmol/liter)	N/A
Hyperphosphatemia	Phosphorus > 4.5 mg/dl (1.5 mmol/liter)	N/A
Hyperkalemia	Potassium > 6 mmol/liter	Cardiac dysrhythmia or sudden death probably or definitely caused by hyperkalemia
Hypocalcemia	Corrected calcium < 7.0 mg/dl (1.75 mmol/liter) or ionized calcium < 1.12 mg/dl (0.3 mmol/liter) [#]	Cardiac dysrhythmia, sudden death, seizure, neuromuscular irritability (tetany, paresthesias, muscle twitching, carpopedal spasm, Trousseau's sign, Chvostek's sign, laryngospasm, or bronchospasm), hypotension, or heart failure probably or definitely caused by hypocalcemia
Acute Kidney Injury [!]	N/A	Increase in the serum creatinine level of 0.3 mg/dl (26.5 µmol/liter) or the presence of oliguria (average urine output of < 0.5 ml/kg/hr over a 6-hour period)

* Laboratory TLS requires two or more metabolic abnormalities must be present during the same 24-hour period within 3 days before the start of therapy or up to 7 days afterward.

** Clinical TLS requires the presence of Laboratory TLS plus one or more findings from the Clinical TLS column.

Corrected calcium = measured calcium level in mg/dl + 0.8 × (4 – albumin in gm/dl).

! Acute kidney injury, unless attributable to another cause, represents clinical TLS even if criteria for laboratory TLS are not satisfied.

Cross reference: Howard SC 2011⁴³

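### Safety SAP Table 6 flags blood pressure only when it is high, so section 7.8.1 gives no count of subjects with low blood pressure and does not list a subject whose only abnormality is low pressure

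*SAP*

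**What the plan says.** Safety SAP 7.8 names four variables: "The vital sign variables that will be assessed are systolic blood pressure, diastolic blood pressure, pulse and temperature". Section 7.8.1 then screens them against fixed limits in Table 6 and produces two outputs:

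- a count and percentage of subjects with "at least one post-baseline observation meeting the pre-defined criteria for potentially clinically significant values will be provided for each variable";
- a listing, described as "a listing of all observations collected will be generated for subjects that had at least one post-baseline observation meeting pre-defined criteria".

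For systolic pressure the only criterion is labelled High ("Value \geq 160 mmHg"), and the same holds for diastolic pressure ("Value \geq 100 mmHg"). Heart rate has a low limit (50 bpm or less) and a high limit (120 bpm or more). Temperature also has both (36°C or less, 38.5°C or more). The SAP gives no reason for the difference.

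The protocol plans a second analysis. Section 8.1.4.4 covers change from baseline at scheduled visits and at the final visit for blood chemistry and hematology, "as well as urinalysis and vital sign parameters". It does not restrict direction. The safety SAP does not describe this analysis for vital signs.

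On hypotension, protocol 3.3 reports serious events in the 32-subject AML monotherapy study that include "failure to thrive, renal failure acute, and hypotension (2 subjects each"). Appendix H, in its clinical tumor lysis column, includes "hypotension, or heart failure probably or definitely caused by hypocalcemia". Appendix E also gives hypotension as an example symptom of hypocalcemia.

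**The concern.** Section 4.0 of the safety SAP says that the effect of treatment on vital signs will be assessed. For blood pressure, the one screen it specifies looks only upward. The documents tie the downward direction to clinical tumor lysis syndrome, and protocol 3.0 names that syndrome as an important identified risk of venetoclax.

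The adverse event tables are not a measured screen. Under protocol 6.1.1.1 a change in vital signs becomes an adverse event only if it leads to discontinuation from the study, needs treatment, meets a protocol criterion, or is judged to be one by the investigator. A low reading that passes none of these tests leaves no trace in the adverse event data. A reader of a Table 6 report who saw few subjects with notable blood pressure values would have learned nothing about low values.

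**Working it through.** No sample size, power or event figure is involved, so the check is a reading of Table 6 against the other places where low pressure could surface.

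**Step 1. Rows of Table 6.**

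| Variable | Low criteria | High criteria |
|---|---|---|
| Systolic pressure | 0 | 1 |
| Diastolic pressure | 0 | 1 |
| Heart rate | 1 | 1 |
| Temperature | 1 | 1 |
| Total | 2 | 4 |

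There are 2 + 4 = 6 criteria. A subject whose only abnormality is low pressure meets 0 of 6, so is neither counted nor listed.

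**Step 2. Could a row have been lost in reading the PDF?** For heart rate and temperature, the variable name stands on the Low row and the High row follows with a blank name. For both pressures the name stands on the High row. A dropped Low row would be expected to take the name with it. Loss cannot be ruled out entirely, but the layout does not suggest it.

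**Step 3. Other routes in the plan.**

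- *Listing under 7.8.1.* It prints every observation of a flagged subject. Low pressures therefore appear if that subject was flagged on another criterion, such as heart rate or temperature. They are shown but not counted.
- *Change from baseline, protocol 8.1.4.4.* It works by scheduled visit and averages readings taken on the same day. With k readings in a day, one of which falls by d while the others are unchanged, the daily value falls by d/k. If visits are summarized by means (an assumption, since the section does not name the statistic), that subject moves the mean of n subjects by d/(kn). At n = 92 this is d/(92k). A short or isolated fall is diluted.
- *Adverse event tables, safety SAP 7.6.1.* Hypotension reported as an adverse event is summarized by preferred term, and again among serious events if it qualifies.
- *Selected adverse events, safety SAP Table 4.* Hypotension is not one of the categories.
- *Laboratory tumor lysis, safety SAP Table 5.* It is defined from uric acid, potassium, phosphorus and calcium only.

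**Step 4. Are the data there?** Protocol Table 3 schedules vital signs at screening, on Day -1, on Cycle 1 Days 1 to 5, on Day 1 of each later cycle, at the final visit and at the 30-day safety visit. Protocol 5.3.1.1 includes blood pressure among them. A low criterion needs no new measurement.

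**Step 5. The one available rate.** Protocol 3.3 gives 2 of 32 subjects with serious hypotension: 2/32 = 0.0625, or 6.3%. The exact (Clopper-Pearson) 95% interval is about 0.8% to 20.8%. This shows that the event occurs with the drug in AML. It does not measure the gap, because it counts reported serious events and not unrecorded low readings.

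**The case against.** The strongest reply is that clinically meaningful hypotension already has routes into the report. If it needs treatment, or the investigator thinks it matters, it is an adverse event and is tabulated. Tumor lysis and Grade 3 or higher infection have their own analyses (safety SAP Tables 4 and 5). Appendix H counts hypotension only when it is attributed to hypocalcemia, and protocol 6.1.8.2 reports no clinical tumor lysis in 94 subjects. Protocol 8.1.4.4 remains in force, and the study is open-label, non-randomized and descriptive. All of this stands, and it is why the point is minor. It does not supply a count of measured low pressures.

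Four stronger readings are tempting, and the documents do not support them:

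- *That hypotension cannot appear anywhere in the vital-sign analysis.* Falls enter 8.1.4.4, and low readings print in the listing of any subject flagged for something else.
- *That about 6 of 92 subjects would have serious hypotension and all would escape Table 6.* The arithmetic is 0.0625 × 92 = 5.75, with a range from 0.008 × 92 = 0.7 to 0.208 × 92 = 19.1. The rate comes from monotherapy in a population that was 94% relapsed or refractory (protocol 3.3), and safety SAP 6.2 expects safety profiles to differ between these regimens. Such subjects could be flagged on heart rate or temperature, and serious events are in the serious adverse event tables. Only this follows: nobody is flagged for low pressure.
- *That the plan misses the expected sign of sepsis.* No section links the two; they merely share a list of serious events in protocol 3.3.
- *That 8.1.4.4 already implies a summary of the largest fall.* It specifies change by visit and at the final visit, on daily averages, and not a minimum value.

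**Conclusion.** The point holds in a limited form. Table 6 has no low criterion for either pressure, so section 7.8.1 yields no count of subjects with low blood pressure and omits from its listing those with no other abnormality. The practical gap is measured low readings that were not recorded as adverse events. Its size cannot be computed, since the documents give no rate for such readings and no low limit.

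The conclusion rests on two assumptions: that Table 6 was read completely, and that the safety SAP describes all the vital-sign analyses intended beyond protocol 8.1.4.4. If the sponsor left out the low limits on purpose, a sentence giving the reason would settle the matter. No efficacy result or dose decision depends on it.

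**What to change.** 1. Add a Low row for systolic pressure and a Low row for diastolic pressure to safety SAP Table 6, at limits the sponsor sets in advance, with the same count and listing as the existing rows. Otherwise, state why low pressure is left out.
2. Carry the vital-sign change-from-baseline analysis of protocol 8.1.4.4 into safety SAP 7.8, so that the two documents agree.

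The cost is two table rows and a short paragraph, using blood pressures already collected. If data have already been seen at an interim report, say so beside the new limits.

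No particular limit is proposed here.
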